## Clinical Investigation Plan (CIP)

Expected duration of each participant's participation	Approximately 30 minutes
Number of participants required to be included in the clinical investigation, and where needed anticipated distribution of enrolment among the participating clinical sites.	30 subjects seen at PARC
Estimated time needed to select this number (i.e. enrolment period).	Approximately 2 weeks
Relationship of investigation population to target population	Investigation population will contain a variety of external auditory canal sizes and shapes, relatable to the average patient without any external auditory canal anomalies.
Information on vulnerable, pregnant and breastfeeding population, if applicable.	N/A

### 6.4 Procedures

#### 6.4.1 Investigation-related Procedure

Three researchers will be facilitating these appointments to limit variability of researcher skill across the two conditions. Researchers will familiarize themselves with the [REDACTED] equipment through independent practice prior to a training facilitated by [REDACTED] (occurring April 23rd) and the researchers will follow [REDACTED] training recommendations (perform scans on 20+ ears following in-person training) prior to data collection. Participants will be seen for one appointment. REUR/REUG, RECD, tympanometry, and reflex thresholds will be collected. The researcher will perform both traditional earmold impressions and 3D ear scans on both ears (conditions will be randomized and counterbalanced across participants). An additional researcher will use a stop watch to quantify the time (mm:ss) it takes for each condition, for both ears. After each procedure, participants and the clinician will also be asked to complete a questionnaire regarding each condition, focusing on their perception of comfort and level of involvement throughout the impression taking. In the event that a clinician feels as though a silicone impression needs to be remade, this will be recorded on the clinician questionnaire. Timing will be recorded for all attempts, but only the time recorded for the final impressions will be used in the data analysis. The resulting data will be compiled for all participants and analyzed using a T-test, to identify any significant differences in the time it takes to complete each method of earmold impressions, in addition to any differences in perceptual comfort.

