## Clinical Investigation Plan (CIP)

### 1.3 Overall synopsis of the clinical investigation

Background and Rationale	
████████ claims the █████ 3D ear scanning solution to streamline clinical processes. According to █████, with the █████, you can:
 
 
• save time and money on handling earmolds and hearing aids
 
• secure digital patient records for easy storage, retrieval and use
 
• ensure a better fit and reduce remakes and returns,
 
• enjoy a cleaner procedure
 
 
████████ ████████ ████████
																	
	
Previous research has been done at Sonova HQ to analyze the quality of █████ ear scans compared to traditional earmold impressions. However, to fully understand the value drivers, further data is needed exploring efficiency and preferences in comparison to traditional EMI methods. In addition, the department of Audiological Care is interested in finding out if this is a viable piece of equipment for their clinics. The results of previous research regarding quality of the █████ has warranted a further look into efficiency and subjective preference.
																	
Investigation Objectives	
The primary objective of this study is to identify any significant differences in the time required for a clinician to complete the workflow of an █████ impression compared to traditional earmold impressions.
 
The secondary objective of this study is to identify any significant preference for both the HCPs and patients when comparing the █████ to traditional EMI procedures.
																	
Outcome(s) / Endpoints:	
Time (mm:ss) will be recorded to quantify the duration of each impression procedure.
 
Questionnaires will be administered to assess overall preferences of both the researchers and subjects.
																	

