## Clinical Investigation Plan (CIP)

	Number of Arms: [2]		
	 Observational Study		
	Investigation Model		Time Perspective
	 Cohort	 Ecologic	 Retrospective
	 Case-Control	 Family-based	 Prospective
	 Case-only	 other:	 Cross-sectional
	 Case-crossover		 other:
	Number of Groups/ Cohorts: [1]		
Type of design	 Exploratory	 Confirmatory	 Observational
Inclusion / Exclusion criteria:	External auditory canal must be present and medically unremarkable to facilitate impressions. Participants with surgical ears or without external auditory canals must be excluded.		
Measurements and procedures:	Three researchers will be facilitating these appointments to limit variability of researcher skill across the two conditions. Researchers will familiarize themselves with the [REDACTED] equipment through independent practice prior to a training facilitated by [REDACTED] (occurring April 22nd) and will follow [REDACTED] training recommendations (perform scans on 10+ ears following in-person training) prior to data collection. Participants will be seen for one appointment. The researcher will perform both traditional earmold impressions and 3D ear scans on both ears (conditions will be randomized and counterbalanced across participants). An additional researcher will use a stop watch to quantify the time (mm:ss) it takes for each condition, for both ears. At the end of the appointment, participants will also be asked to complete a subjective questionnaire regarding each condition, focusing on their perception of comfort and level of involvement throughout the impression taking. The resulting data will be compiled for all participants and analyzed using a T-test, to identify any significant differences in the time it takes to complete each method of earmold impressions, in addition to any differences in subjective domains.		
Intervention:	[REDACTED] 3D Ear Scanning Solution		
Control Intervention (if applicable):	Traditional silicone earmold impression material, administered by a cartridge impression gun.		

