### 5 Objectives and hypotheses of the clinical investigation

#### 5.1 Purpose of the clinical investigation claims for clinical performance, effectiveness or safety of the investigational device that are to be verified

The purpose of this study is to better understand the value drivers behind the [REDACTED]. The study intends to find any significant difference in the time it takes to complete the workflow of the [REDACTED] 3D ear scanner impressions, compared to a traditional silicone earmold impression (EMI). A secondary purpose of this study is to identify preferences between the [REDACTED] and traditional methods, for both patients and providers. This information will allow us to find out whether this is a viable piece of equipment for Audiological Care clinics.

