#### 5.2 Primary and Secondary Objectives

The Primary objective is to identify any significant differences in the time required for a provider to complete the workflow of an [REDACTED] 3D ear scanner, compared to traditional silicone earmold impression procedures. The secondary objective is to identify any significant preferences for both providers and patients.

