##### 6.1.3 Endpoints with rationale for their selection and measurement

To satisfy the primary objective, the entirety of the procedural workflow will be captured using a stop watch (mm:ss) for both conditions, in order to have a direct measure of the timing component of the investigation. To satisfy the secondary objective, subjective questionnaires will be administered to answer questions relevant to incorporating this product into clinics. Question domains will include, but are not limited to, patient comfort, patient's perceived level of involvement, researcher's ease of use, and both patient/provider confidence in the scan/impresion producing an appropriate earmold.

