## Clinical Investigation Plan (CIP)

- Introduction – “I will be taking some impressions of your ear canals. I will place this foam block in each ear, before filling your canals with the silicone impression material. It will take a few minutes to harden before I remove them. Due to the nature of this study, I am going to ask you to hold any questions until after the procedure is done, but do not hesitate to let me know if you are experiencing any discomfort throughout the procedure.”
- Have materials out and ready to go (impression cartridge in impression gun, box folded together, but do not put a tip on the impression gun)
- Otoscopy
- Cerumen management if needed
- Start timer
- Tie off otoblocks
- Place otoblocks bilaterally
- Confirm otoblock placement with otoscopy
- Put tip on impression gun
- Administer impression material bilaterally
- Check hardness of silicone every 30 seconds
- Remove impressions when set
- Inspect impressions for landmarks
- Perform otoscopy
- Put impressions in box
- End timer
- Administer questionnaires

- Introduction – “I will be using this camera to take some scans of your ear canals. I will place a headset on you and this probe will be inserted into your canal. You will be able to view the procedure on the TV in front of you. Due to the nature of this study, I am going to ask you to hold any questions until after the procedure is done, but do not hesitate to let me know if you are experiencing any discomfort throughout the procedure.”
- Otoscopy
- Start timer
- Sanitize [REDACTED] tip and headset
- Enter patient info
- Hair management
- Headset placement
- Perform scans bilaterally
- Inspect scans for landmarks
- Press power button on screen to save scans
- End timer
- Administer questionnaires

**IN THE EVENT THAT A CLINICIAN FEELS AS THOUGH THE IMPRESSION/SCAN IS UNSATISFACTORY TO SEND IN FOR A CUSTOM PRODUCT, THE PROCEDURE WILL BE REPEATED. THE TIMING OF ALL PROCEDURES WILL BE RECORDED ON THE TIMING**

SRF-371

SKP-371

Confidential and proprietary.  
This document and its contents are confidential and proprietary to Sonova and shall not be reproduced or otherwise disclosed to anyone other than Sonova employees without written authorization from Sonova.

This printout is an uncontrolled copy. The original is stored in the Document Management System.  
Template: TPL-368 [2]

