#### 7.3.1 Datasets to be analyzed, analysis population

Total procedure time will be recorded in seconds. Each procedure time will be recorded along with the audiologist, the anonymous participant ID, the procedure methodology (i.e., scanning or traditional silicone impressions), and the ordinal number of the procedure for the given methodology by the respective audiologist. Qualitative data will be collected as a question, response, methodology, and anonymous participant ID.

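### Only the final attempt's time is analysed, so no planned analysis measures the time to complete the workflow when an impression or scan is repeated

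*Combined protocol and SAP*

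**What the plan says.** Section 5.2 makes the primary objective a comparison of "the time required for a provider to complete the workflow" between the scanner and silicone. Section 6.1.3 gives the matching endpoint: "the entirety of the procedural workflow will be captured using a stop watch (mm:ss) for both conditions". The synopsis (1.3) words the outcome more narrowly: "Time (mm:ss) will be recorded to quantify the duration of each impression procedure".

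The timing details in 6.4.1 deal with failures. If the clinician judges that "THE IMPRESSION/SCAN IS UNSATISFACTORY TO SEND IN FOR A CUSTOM PRODUCT, THE PROCEDURE WILL BE REPEATED". Every attempt is timed (6.4.1 and 8.1.1), and the reason for a repeat goes on the clinician questionnaire. The main text of 6.4.1 then sets the analysis rule: "Timing will be recorded for all attempts, but only the time recorded for the final impressions will be used in the data analysis".

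The statistical section does not restate that rule. Section 7.3.1 says "Total procedure time will be recorded in seconds", without saying whether attempts are summed. It lists audiologist, participant ID, methodology, and the sequence number of the procedure for that audiologist and methodology. Section 7.3.2 regresses procedure time on methodology with a random audiologist effect. Section 7.3.3 rules out statistical analysis of the questionnaires and allows only an optional visual look at learning curves.

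**The concern.** A clinician who rejects a first impression or scan has not finished. The workflow ends when there is a product fit to send in, and the time spent on the rejected attempt is part of the time taken. The plan measures that time and then leaves it out of the analysis.

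If one method fails more often, or its failures cost more time, the final-attempt comparison flatters it. Section 3.2 names procedural time as a value driver for the clinics' decision on the scanner, and the synopsis cites the device maker's claim of fewer remakes. That claim may refer to finished products, but it shows that repeated work is part of the value question. A cumulative analysis added after the results are seen would be post hoc.

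**Working it through.** **1. Text against text.**

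| Element | Where | What it implies |
|---|---|---|
| Objective | 1.3, 5.2 | time to complete the workflow |
| Endpoint | 6.1.3 | the whole procedural workflow |
| Repeat rule | 6.4.1, timing details | an unsatisfactory attempt is redone |
| Data recorded | 6.4.1, 8.1.1 | time of every attempt |
| Data analysed | 6.4.1 | time of the final attempt only |
| Model | 7.3.2 | procedure time by methodology; no cumulative or repeat term |
| Other analyses | 7.3.3 | optional visual learning curve; questionnaires not analysed |

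The separate one-time recording described at the end of the timing details covers set-up and ordering, not repeats. The sequence number in 7.3.1, together with participant ID and methodology, would identify repeats if each repeat is logged as its own procedure, but the plan does not say that it is.

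**2. Size of the shift.** The plan has no figure of its own to reproduce here. Inputs from the documents are N = 30 with both methods in each participant (1.3) and about 15 minutes per method (6.2). Repeat rates are assumed, as is 7.5 minutes for a shorter repeat, and each participant has at most one repeat per method.

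- Shift per extra repeat in one method = d / 30: 15/30 = 0.50 min; 7.5/30 = 0.25 min.
- Shift for a gap in repeat rates = d × gap. For d = 15: 15 × 0.10 = 1.5 min and 15 × 0.20 = 3.0 min. For d = 7.5: 0.75 and 1.5 min.
- Equal rates and equal durations: shift 0, although both absolute times are understated.
- Chance of at least one repeat among 30 at an assumed 5% rate: 1 − 0.95^30 = 78.5%. At 10% it is 95.8%.

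For scale, a paired t-test with 30 pairs, two-sided 0.05 and 80% power detects 2.65 min if the SD of the differences is 5 min (assumed). The omitted part can be of similar size.

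The sign can also change. Assume mean attempts of 8 min (scan) and 10 min (silicone), 30% scan repeats and no silicone repeats. The final-attempt difference is 8 − 10 = −2 min; the cumulative difference is 8 × 1.3 − 10 = +0.4 min.

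**3. Precision of a cumulative analysis.** Assume a final-attempt paired SD of 5 min (the synopsis mentions roughly 5 minutes but does not define it as an SD), 5% repeats in one method, and p = 15% or 25% in the other.

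Paired SD = √(25 + d² × [p(1 − p) + 0.05 × 0.95]); half-width = t(0.975, 29) × SD/√30, with t = 2.045.

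| d (min) | p | SD (min) | 95% half-width (min) |
|---|---|---|---|
| no repeats | – | 5.00 | 1.87 |
| 15 | 15% | 8.02 | 3.00 |
| 15 | 25% | 8.82 | 3.30 |
| 7.5 | 15% | 5.90 | 2.20 |
| 7.5 | 25% | 6.18 | 2.31 |

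A simulation of 40,000 trials of 30 pairs with no true final-attempt difference agrees. The final-attempt difference averaged about 0.00. The cumulative difference averaged 1.50 and 3.00 min (d = 15) and 0.75 and 1.49 min (d = 7.5). Interval coverage was about 95% in each case. These half-widths are for a paired t-interval, not for the mixed model in 7.3.2.

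**The case against.** The strongest reply is that the workflow has an operational definition. The timing details list the steps between starting and stopping the timer, and the synopsis defines the outcome per procedure. On that reading one complete pass is the target, and the final attempt measures it. This stands in part: time per accepted attempt is a legitimate quantity. It does not by itself answer a question about completing the workflow when the plan requires unsatisfactory attempts to be redone.

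Second, the final-attempt rule appears only in 6.4.1, which also names a t-test where 7.3.2 plans a mixed model, and the total time in 7.3.1 might be meant as a sum. But section 7 never says so, and 6.4.1 says the opposite. The sections must be reconciled in any case.

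Third, the rule follows a sentence about remaking silicone impressions and might not reach scans. The documents also call scans impressions (1.3, 5.1), so the broader reading is the natural one. If the rule did cover silicone only, scan repeats would have no stated rule and the methods could be treated unequally.

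Fourth, questionnaire data will be compiled, so repeats could be counted. True, but no section names that count as an output.

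Finally, the study is exploratory, has no power target and retains all attempt times. That lowers the stakes. It does not align the analysis with the objective. It is also true that every repeat rate and SD above is assumed; the finding rests on the text, not on those figures.

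**Conclusion.** The concern holds. As written, the plan analyses time per accepted attempt while its objective is time to complete the workflow, and no planned analysis closes the gap. The comparison is biased as a measure of workflow time whenever the time lost to repeats differs between methods. Direction and size cannot be derived from the documents: the illustrated 0.75 to 3.0 min depends on assumed repeat-rate gaps of 10 to 20 points and repeats of 7.5 to 15 min, and the true shift could be zero. The point should be fixed before analysis. It is not fatal, because the data needed are being collected.

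**What to change.** - In 6.4.1 and 7.3, prespecify an analysis of cumulative timed minutes over all attempts, applied identically to scans and silicone. Use the same model as the final-attempt analysis, and report both on the same time scale so that they can be compared.
- Report it alongside the final-attempt analysis, with the number of repeats by method.
- Base any conclusion about time to complete the workflow on the cumulative result, or limit the conclusion to time per accepted attempt.
- In 7.3.1, define the total time variable accordingly and give each timed record an attempt number.
- In 6.4.1, state that the final-attempt rule covers both methods, and reconcile 1.3, 6.1.3, 6.4.1 and 7.3.1.

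The cost is wording plus one field on the timing record; no new procedure is needed. Cumulative time is more variable and more skewed, and the transformation step in 7.3.2 may not fully remove the skew. Under the assumptions above, the half-width rises from 1.87 min to about 3.0–3.3 min (15 min repeats) or 2.2–2.3 min (7.5 min repeats). Cumulative time also depends on an unblinded clinician's decision to repeat, which is a further reason to report both analyses.

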**The step by step processes for each procedure and corresponding time recording are as follows:**

### **TIMING DETAILS**

#### Silicone EMI

SRF-371

Confidential and proprietary.

This document and its contents are confidential and proprietary to Sonova and shall not be reproduced or otherwise disclosed to anyone other than Sonova employees without written authorization from Sonova.

This printout is an uncontrolled copy. The original is stored in the Document Management System  
 Template: TPL-368 [2]

## Clinical Investigation Plan (CIP)

- Introduction – “I will be taking some impressions of your ear canals. I will place this foam block in each ear, before filling your canals with the silicone impression material. It will take a few minutes to harden before I remove them. Due to the nature of this study, I am going to ask you to hold any questions until after the procedure is done, but do not hesitate to let me know if you are experiencing any discomfort throughout the procedure.”
- Have materials out and ready to go (impression cartridge in impression gun, box folded together, but do not put a tip on the impression gun)
- Otoscopy
- Cerumen management if needed
- Start timer
- Tie off otoblocks
- Place otoblocks bilaterally
- Confirm otoblock placement with otoscopy
- Put tip on impression gun
- Administer impression material bilaterally
- Check hardness of silicone every 30 seconds
- Remove impressions when set
- Inspect impressions for landmarks
- Perform otoscopy
- Put impressions in box
- End timer
- Administer questionnaires

- Introduction – “I will be using this camera to take some scans of your ear canals. I will place a headset on you and this probe will be inserted into your canal. You will be able to view the procedure on the TV in front of you. Due to the nature of this study, I am going to ask you to hold any questions until after the procedure is done, but do not hesitate to let me know if you are experiencing any discomfort throughout the procedure.”
- Otoscopy
- Start timer
- Sanitize [REDACTED] tip and headset
- Enter patient info
- Hair management
- Headset placement
- Perform scans bilaterally
- Inspect scans for landmarks
- Press power button on screen to save scans
- End timer
- Administer questionnaires

**IN THE EVENT THAT A CLINICIAN FEELS AS THOUGH THE IMPRESSION/SCAN IS UNSATISFACTORY TO SEND IN FOR A CUSTOM PRODUCT, THE PROCEDURE WILL BE REPEATED. THE TIMING OF ALL PROCEDURES WILL BE RECORDED ON THE TIMING**

SRF-371

SKP-371

Confidential and proprietary.  
This document and its contents are confidential and proprietary to Sonova and shall not be reproduced or otherwise disclosed to anyone other than Sonova employees without written authorization from Sonova.

This printout is an uncontrolled copy. The original is stored in the Document Management System.  
Template: TPL-368 [2]

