## Clinical Investigation Plan (CIP)

### 6.2 Investigational device(s) and comparator(s)

Description of the exposure to the investigational device(s)	For each subject, the investigational device (█████ 3D ear scanner) will have an exposure time of approximately 15 minutes, or the length of time it takes to complete a 3D ear scan in its entirety.
Description of the exposure to the comparator(s), if used.	For each subject, the comparator (silicone earmold impression procedure) will occur for approximately 15 minutes, or the length of time it takes to complete a traditional silicone earmold impression.
List of any other medical device to be used during the clinical investigation (if applicable)	N/A
Number of investigational devices to be used, and justification	1 – The investigational device can be reused and sanitized between subjects in accordance with the manufacturer recommendations.

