# Clinical Investigation Plan (CIP)

## RECORDS, AND REASON FOR REPEAT WILL BE CAPTURED IN THE CLINICIAN QUESTIONNAIRE.

These timing details do not include setting up equipment (removing from drawers/cabinets, etc.), sending a silicone impression order through the eStore, or sending [REDACTED] scans to a manufacturer. One researcher ([name]) will take a one-time time recording of these processes and others that may be of interest, separate from data collection.

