## Clinical Investigation Plan (CIP)

each methodology will be tested for normality using a Shapiro-Wilk test. If the data are normally distributed, additional analysis will proceed immediately. If data are not normally distributed, transformation(s) may be performed on the data, as appropriate, to achieve an approximately normal distribution of the response data for further analysis.

Data (raw or transformed, per above) will then be subjected to analysis via linear mixed effects modeling. The model will be constructed to regress (raw or transformed) procedure time on a dummy variable of methodology (fixed effect), with a random effect of audiologist. This model will allow the investigators to evaluate the relative difference in procedure time between the methodologies, while removing and separately evaluating the variance contributed by the audiologist undertaking the procedure.

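### Cartridge loading and box folding are off the silicone clock while scanner sanitising and patient-data entry are on the scan clock; these placements raise scanner minus silicone by an unstated amount, and the net over all unmatched steps is open

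*Combined protocol and SAP*

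**What the plan says.** Section 6.4.1 (Timing Details) gives one ordered list per method, each with a start and an end for the timer.

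- **Silicone, before the start:** "Have materials out and ready to go (impression cartridge in impression gun, box folded together", with the qualifier "but do not put a tip on the impression gun". Initial otoscopy and any cerumen management are also before the start.
- **Silicone, after the start:** the first timed step is "Tie off otoblocks". Placing the blocks, fitting the gun tip, the impression itself, a closing otoscopy and boxing follow.
- **Scan, before the start:** otoscopy.
- **Scan, after the start:** sanitising the tip and headset, then "Enter patient info", hair management, headset placement, scanning, inspection and saving.

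After the lists, section 6.4.1 excludes equipment set-up, placing a silicone order and sending scans from the timing. One researcher "will take a one-time time recording of these processes and others that may be of interest, separate from data collection".

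Sections 4.6, 6.1.3, 6.1.4 and 6.1.5 describe the primary measure as covering the whole procedural workflow in both conditions. For the dataset, section 7.3.1 says: "Total procedure time will be recorded in seconds". Section 7.3.2 regresses that time on method, "with a random effect of audiologist".

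**The concern.** The primary question is whether one method takes longer than the other, and the answer informs whether clinics adopt the scanner. If readying the equipment is counted for one method and left out for the other, part of the recorded difference reflects where the timer was started. Such an offset belongs to the method, so more participants, order balancing or several audiologists do not average it away. The plan gives no reason for where the start points lie, and a reader told that the whole workflow was timed would not expect the difference.

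**Working it through.** **Step 1. Set the lists side by side** (section 6.4.1).

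| Step | Silicone | Scan | Effect of the placement on scanner minus silicone |
|---|---|---|---|
| Cartridge loading, box folding | before start | none | raises |
| Sanitising, patient-data entry | none | timed | raises |
| Otoblock tying, gun-tip fitting | timed | none | lowers |
| Closing otoscopy | timed | not listed | lowers |
| Cerumen management if needed | before start | not listed | raises, if counted as silicone work |
| Set-up, ordering, sending | untimed | untimed | cannot be derived |

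The first two rows, which hold the four named steps, have a known sign. The table as a whole does not.

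**Step 2. Write the offset out.** Per participant let S be the untimed silicone preparation (cartridge loading, box folding), Q the timed silicone preparation (otoblock tying, tip fitting), P the timed scan preparation (sanitising, patient-data entry) and W the remaining timed work.

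- Recorded: D = (P + W_scan) − (Q + W_sil)
- All listed preparation counted: D_all = (P + W_scan) − (S + Q + W_sil) = D − S
- No preparation counted: D_none = W_scan − W_sil = D − (P − Q)

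S cannot be negative, so D is at least as large as D_all. P − Q can have either sign. The documents give no duration for P, Q or S, so neither offset can be computed, and there is no plan figure to reproduce.

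**Step 3. Follow it through the model.** The method coefficient in section 7.3.2 estimates D. Each audiologist performs both methods, so an audiologist effect cancels from the comparison, whereas a term present in one method only does not. Counterbalancing balances order, which is unrelated to which steps are timed.

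**Step 4. Illustrate the size.** The 30 participants with both methods come from the synopsis. Assumed: two-sided 5% level, a constant net offset b of 0.25, 0.5 or 1 min, and an SD of 5 or 3 min. The synopsis mentions approximately 5 minutes without saying whether that is an SD, a variance or a range. Against the approximately 15 min per procedure in section 6.2, these offsets are 0.25/15 = 1.7%, 0.5/15 = 3.3% and 1/15 = 6.7%.

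Coverage of the 95% interval for the like-for-like difference = 1 − P(|T| > t_crit), with T noncentral t and noncentrality b/SE. It is the same for either sign of b.

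- Mixed model, audiologist effect only, about 56 df, a participant's two times taken as uncorrelated: SE = SD × √(2/30). SD 5 gives SE 1.291 and half-width 2.59 min; SD 3 gives 0.775 and 1.55 min.
- The t-test named in the synopsis and section 6.4.1, assumed to be paired, 29 df: SE = SD of differences/√30. SD 5 gives 0.913 and 1.87 min; SD 3 gives 0.548 and 1.12 min.

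| Analysis | SD (min) | b = 0.25 | b = 0.5 | b = 1 |
|---|---|---|---|---|
| Mixed model | 5 | 94.6% | 93.3% | 88.1% |
| Mixed model | 3 | 93.8% | 90.3% | 75.5% |
| Paired t | 5 | 94.2% | 91.7% | 81.5% |
| Paired t | 3 | 92.7% | 85.7% | 57.7% |

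In the mixed model with SD 5, the offset is 10%, 19% or 39% of the half-width (0.25, 0.5 or 1 divided by 2.59). If the like-for-like times are equal, the false-positive rate is 1 − coverage, for example 6.7% at b = 0.5 in the first row. The point estimate moves by the whole of b in every row.

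**The case against.** The lists define what is timed, and the exclusion of equipment set-up is disclosed. A loaded cartridge and a folded box can be read as set-up, and leaving the gun tip off until the timer runs suggests a considered boundary. Section 6.2 says of the scanner: "The investigational device can be reused and sanitized between subjects in accordance with the manufacturer recommendations". Sanitising therefore recurs with each participant, while nothing states how often a cartridge is loaded, so part of the imbalance may be a real difference between methods. For the difference in listed, timed steps there is no bias; the like-for-like difference used above is not an estimand in the plan. The study is exploratory, and every offset and SD in the illustration is assumed. All of this stands and limits the weight of the point.

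Two stronger readings are tempting.

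- A reader might infer that the trial as a whole is biased against the scanner. The four named steps do work that way, but otoblock tying, tip fitting and the closing otoscopy work the other way, and no durations are given.
- A reader might infer that the gap cannot be closed once the data are in. A constant offset in a mean difference can be subtracted if it is estimated separately, and the untimed silicone steps need no participant, so they can be timed at any point.

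What remains is that the planned recording is made once by one researcher, does not name cartridge loading or box folding, and has no stated use in the analysis. The timed preparation cannot be split out of a stored total. As planned, only a rough correction is possible.

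**Conclusion.** The start points are unmatched and no reason is given for them. The four named placements raise scanner minus silicone; the net sign and size over all unmatched steps cannot be derived. Whatever the offset is, the method coefficient carries it in full. Under the assumptions shown, the consequence runs from negligible (94.6% coverage) to serious (57.7%, which needs a 1 min net offset, an SD of differences of 3 min and the paired test). Small offsets barely change the test result; the estimate is what shifts.

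Separately from its size, the description in sections 4.6 and 6.1.3 to 6.1.5 is broader than what section 6.4.1 times, and the two must be reconciled. The point does not invalidate the trial, but the change should be made, because it is cheap and part of it is possible only before data collection.

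**What to change.** Before the first participant:

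1. Keep the listed start and end points as the primary time. Have the timekeeper, who is already present, log laps for the timed preparation: otoblock tying and tip fitting for silicone, sanitising and patient-data entry for the scan. Add these fields to section 7.3.1.
2. In the separate recording described in section 6.4.1, name cartridge loading (with how often it occurs) and box folding, and repeat the recording several times per audiologist.
3. Pre-specify two sensitivity analyses of the scanner-silicone difference: without preparation (D − (P − Q), from the laps), and with the untimed silicone preparation added (D − S, from the separate recording). Make both adjustments on the raw times, before any transformation under section 7.3.2.
4. In sections 4.6, 6.1.3, 6.1.4 and 6.1.5, replace the claim of whole-workflow timing with a list of what is timed and what is excluded: set-up, ordering, sending, initial otoscopy and cerumen management, as well as cartridge loading and box folding.

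The cost is a few more fields on the timing form and in the dataset, a short repeated recording, and one lap (tip fitting) logged in mid-procedure. How either procedure is performed does not change.
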